### **11.1.1 Time-to-event definition**

Progression-Free Survival (PFS) is defined as the duration of time from start of treatment to time of objective disease progression (including initiation of new therapy or death).

## **12. DATA REPORTING / REGULATORY REQUIREMENTS**

Adverse event lists, guidelines, and instructions for AE reporting can be found in Section 7.0 (Adverse Events: List and Reporting Requirements).

### **12.1 Data Reporting**

#### **12.1.1 Method**

CTRIO/ODQ will collect, manage, and perform quality checks on the data for this study.

#### **12.1.2 Responsibility for Data Submission**

Investigative sites within DF/HCC or DF/PCC are responsible for submitting data and/or data forms to the CTRIO/ODQ according to the schedule set by the CTRIO/ODQ.

### **12.2 Data Safety Monitoring**

The DF/HCC Data and Safety Monitoring Committee (DSMC) will review and monitor toxicity and accrual data from this study. The committee is composed of clinical specialists with experience in oncology and who have no direct relationship with the study. Information that raises any questions about participant safety will be addressed with the Overall PI and study team.

The DSMC will review each protocol up to four times a year or more often if required to review toxicity and accrual data. Information to be provided to the committee may include: up-to-date participant accrual; current dose level information; DLT information; all grade 2 or higher unexpected adverse events that have been reported; summary of all deaths occurring with 30 days of intervention for Phase I or II protocols; for gene therapy protocols, summary of all deaths while being treated and during active follow-up; any response information; audit results, and a summary provided by the study team. Other information (e.g. scans, laboratory values) will be provided upon request.

After the first six participants are accrued to the Phase II cohort, enrollment will be held to conduct a DSMC safety analysis of the first two cycles of treatment.

### **12.3 Multicenter Guidelines**

Not applicable.

## 12.4 Collaborative Agreements Language

Not applicable.

## 13. STATISTICAL CONSIDERATIONS

This is a phase I/II, dose-escalating, single-arm, open-label prospective study aimed at evaluating the safety of ulocuplumab, an anti-CXCR4 monoclonal antibody, in symptomatic patients with CXCR4 mutated WM. As a phase I study, response and/or survival outcomes will not be taken into account for sample size purposes. Regarding toxicity, assuming that an adverse event associated with study drug has a true incidence of 10%, with an estimated sample size of 38 patients (maximum population to be enrolled), the likelihood of observing at least 1 adverse event would be at least 90%

### 13.1 Study Design/Endpoints

This is a phase I/II, dose-escalating, single-arm, open-label prospective study aimed at evaluating the safety of ibrutinib combined with ulocuplumab, an anti-CXCR4 monoclonal antibody, in patients with symptomatic CXCR4 mutated WM. Toxicity will be graded according to the Common Terminology Criteria for Adverse Events (CTCAE version 4.0), which is available at [http://evs.nci.nih.gov/ftp1/CTCAE/CTCAE\\_4.03\\_2010-06-14\\_QuickReference\\_8.5x11.pdf](http://evs.nci.nih.gov/ftp1/CTCAE/CTCAE_4.03_2010-06-14_QuickReference_8.5x11.pdf).

The following will be considered a DLT if occurring during the 1st or 2nd Cycle of Therapy

- $\geq$  Grade 4 hematologic toxicity (anemia, neutropenia, or thrombocytopenia)
- Any grade 5 hematologic or non-hematologic toxicity
- Any grade 4 non-hematologic toxicity, including vomiting or diarrhea
- Any other  $\geq$  Grade 3 adverse event not due to underlying disease, except for Grade 3 infection, easily reversible asymptomatic laboratory abnormalities, and nausea, vomiting, or diarrhea controlled by medications.
  - Grade 3 vomiting or diarrhea can only be excluded if the participant does not require total parenteral nutrition (TPN), tube feeding, or hospitalization, and the toxicity resolves to less than grade 3 within 72 hours.
  - Reversible asymptomatic laboratory abnormalities may be excluded only if they are correctable to <grade 3 within 72 hours.

The following will NOT be considered a DLT

- An IgM flare, which is commonly observed with antibody therapy in WM patients and may require plasmapheresis.
- Lymphocytosis, or mobilization of leukocytes which often occurs as a consequence of CXCR4 antagonism.
- Lymphopenia, which is an intended consequence of therapy.
- A  $\leq$  Grade 2 infusion reaction.

The maximum tolerated dose (MTD) will be the dose below that which produced a DLT or the maximum dose allowed by protocol (1600 mg) if no DLT was observed. The MTD will be then

be used for the phase II portion of the study.

Dose escalation will be as follows, for a maximum accrual of 18 patients:

Number of Participants with DLT at a Given Dose Level	Escalation Decision Rule
0 out of 3	Enter 3 participants at the next dose level.

## 13.2 Sample Size, Accrual Rate and Study Duration

A maximum of 18 patients will be accrued for the phase I study.

A maximum of 20 evaluable patients will be accrued for the phase II study. To be evaluable for response, patients must have one cycle of therapy. Patients inevaluable for response will be replaced. Assuming an H0 of major response rate of 50% vs. an H1 of 80%, a sample of 20 patients would have a power of 80% with an alpha of 0.04 to detect a difference. If 15 patients or more obtain a major response, then the study would be a success, if 14 patients or fewer obtain a major response, then the study would be a failure and the combination should not continue further evaluation. Sample size and power estimation were obtained using the binomial method (STATA version 13).

Accrual time will be approximately 12-18 months, at a rate of 2-3 patients per month. Patients will be followed for the duration of time on active protocol therapy (47 cycles), and then 2 additional years after completion of cycle 47. Participants will be followed for up to 24 months after completion of protocol therapy, or until termination from study, disease progression, initiation of new anti-neoplastic therapy, or death. Participants removed from protocol therapy for unacceptable adverse event(s) will be followed until resolution of the adverse event to at least grade 1 or less, or stabilization of the adverse event.

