## **1.2 Primary Objectives**

- Phase I: To determine the maximum dose or maximum tolerated dose (if a dose-limiting toxicity is identified) of ulocuplumab with ibrutinib in symptomatic patients with CXCR4 mutated WM.
- Phase II: To determine the major response rate (>50% reduction in disease burden) in patients with CXCR4 mutated WM.

[figure not shown]

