### 2.1 Study Disease

Waldenström's macroglobulinemia (WM) is a malignant B-cell lymphoma associated with the accumulation of clonal lymphoplasmacytic cells and monoclonal IgM secretion. Whole genome sequencing has revealed activating somatic mutations in MYD88 and the C-terminal domain of CXCR4 in WM ([name] et al, 2012; Hunter et al, 2014; [name] et al, 2015a). In WM cells, mutated MYD88 triggers NFKB activation via two divergent pathways involving Bruton's tyrosine kinase (BTK) and IRAK1/IRAK4 (Yang et al, 2013). Ibrutinib is an orally administered, small molecule inhibitor of BTK, which triggers apoptosis of mutated MYD88 expressing WM cells. In a multicenter prospective study, 63 symptomatic previously treated WM patients received single agent ibrutinib. The median prior therapies for these patients was 2 (range 1-9), and 40% were refractory to their prior therapy. Patients received ibrutinib (420 mg) until progression or unacceptable toxicity ([name] et al, 2015b). Post-therapy, at best response, median serum IgM levels (used to measure disease burden) declined from 3,520 to 880 mg/dL; hemoglobin rose from 10.5 to 13.8 g/dL; and the bone marrow disease involvement declined from 60% to 25% (p<0.01 for all comparisons). The median time to a minor response ( $\geq 25\%$  reduction in serum IgM) was 4 weeks, and to a major ( $>50\%$  reduction in serum IgM) was 8 weeks. Overall and major response rates were 90.5% and 73.0%, and were highest in patients with MYD88L265PCXCR4Wild-Type (WT) (100% and 91.7%), followed by MYD88L265PCXCR4WHIM (85.7% and 61.9%), and MYD88WTCXCR4WT (60% and 0%) ([name] et al, 2015b). No complete responses were observed. Ten patients achieved a VGPR (15.8%), 8 of whom had CXCR4WT disease. Patients with MYD88L265PCXCR4WHIM showed delayed major response kinetics ( $>6$  months) in comparison to patients with the MYD88L265PCXCR4WT genotype (Figure 1; [name] et al, 2015b).

**Figure 1.** Kinetics of response to single agent ibrutinib in previously treated WM patients stratified by MYD88 and CXCR4 mutation status. Taken from [name] et al, 2015b.

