A multicenter, prospective study of single agent ibrutinib investigated the safety and efficacy of ibrutinib in relapsed or refractory WM patients ([name] et al, 2015b). The median number of prior therapies for these patients was 2 (range 1-9), and 40% of patients were refractory to their previous therapy. Seventy-eight percent of patients had a moderate-high WM IPSS prognostic score. Post therapy, the median serum IgM levels for all 63 patients declined from 3,520 to 880 mg/dL at best response ( $p < 0.01$ ). Pre-therapy, 46/63 (73.0%) patients had a serum IgM  $\geq 3,000$  mg/dL; following treatment, at best response, 6/63 (9.5%) patients had a serum IgM  $\geq 3,000$  mg/dL ( $p < 0.01$ ). Median BM involvement decreased from 60% to 25% ( $p < 0.01$ ), while hemoglobin increased from a median of 10.5 to 13.8 g/dL at best response ( $p < 0.01$ ). Responses included very good partial response (n=10); partial response (n=36); and minimal response (n=11) for overall and major responses of 90.5% (95% CI 80.4%-96.4%) and 73.0% (95% CI 60.3-83.4%), respectively. The median time to at least minor and partial responses were 4 and 8 weeks, respectively. Overall responses were similar regardless of baseline age (<65 vs.  $\geq 65$  years), ECOG status (0 vs.  $\geq 1$ ), pre-therapy Waldenström's macroglobulinemia International Prognostic Scoring System (IPSS) score, serum  $\beta_2$ -microglobulin levels (<3.0 vs.  $>3.0$  mg/L), hemoglobin (<11 vs.  $>11$  g/dL), serum IgM (<4,000 vs.  $\geq 4,000$  mg/dL), BM disease involvement (<50% vs.  $\geq 50\%$ ), prior relapsed or refractory status, and prior lines of therapy (1-3 vs.  $>3$ ), as well as for major responses across most of the baseline subgroups ([name] et al, 2015b). Overall and major response rates were 90.5% and 73.0%, and were highest in patients with MYD88L265PCXCR4Wild-Type (WT) (100% and 91.7%), followed by MYD88L265PCXCR4WHIM (85.7% and 61.9%), and MYD88WTCXCR4WT (60% and 0%) ([name] et al, 2015b). No complete responses were observed. Ten patients achieved a VGPR (15.8%), 8 of whom had CXCR4WT disease. Patients with MYD88L265PCXCR4WHIM showed delayed major response kinetics ( $>6$  months) in comparison to patients with the

MYD88L265PCXCR4WT genotype (Figure 1; [name] et al, 2015b).

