## 2.4 Rationale

CXCR4 is expressed on WM cells (Ngo et al, 2008, Rocarro et al, 2014) and dysregulation of CXCR4 path signaling is common in WM (Hunter et al, 2016). Up to 40% of WM patients harbor a somatic activating mutation that supports tumor growth and survival, as well as drug resistance against many agents used to treat WM in response to its ligand CXCL12 (Hunter et al, 2014; Cao et al, 2014; Rocarro et al, 2014; Cao et al, 2015). CXCR4 mutations are almost always expressed in WM patients with mutated MYD88, and are associated with loss of genes that regulate MYD88 signaling (Hunter et al, 2016). Gene overexpression of CXCL12 has also been observed in WM cells regardless of CXCR4 mutation status, and contributes to enhanced CXCR4 signaling (Hunter et al, 2016). The use of CXCR4 antagonists may therefore offer a targeted approach to therapy of WM patients with WHIM-like somatic mutations. It is thus hypothesized that ulocuplumab will improve overall and major responses, and response kinetics to ibrutinib in symptomatic patients with CXCR4 mutated WM.

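### Phase II tests major response against a 50% null, below the 61.9% the protocol reports for ibrutinib alone in the same genotype

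*Combined protocol and SAP*

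**What the plan says.** Section 13.2 sets the Phase II test: "Assuming an H0 of major response rate of 50% vs. an H1 of 80" percent, and "a sample of 20 patients would have a power of 80% with an alpha of 0.04 to detect a difference". The decision rule follows: "If 15 patients or more obtain a major response, then the study would be a success". With 14 or fewer, the combination is not to be evaluated further. The section gives no source or reason for 50% and does not say whether alpha is one- or two-sided.

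The background supplies a figure for the backbone alone. Section 2.1 describes a study in which "63 symptomatic previously treated WM patients received single agent ibrutinib" at 420 mg. Its overall and major response rates by genotype, repeated under Clinical Efficacy in Section 2.3, include "followed by MYD88 L265P CXCR4 WHIM (85.7% and 61.9" percent. Section 3.1.2 restricts this trial to that genotype (MYD88 and CXCR4 mutated), and Section 1.1 gives every participant ibrutinib at the same 420 mg per day.

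Section 2.4 states the scientific aim: "It is thus hypothesized that ulocuplumab will improve overall and major responses, and response kinetics to ibrutinib". The Phase II primary objective in Section 1.2 is worded more neutrally: "To determine the major response rate (>50% reduction in disease burden) in patients with CXCR4 mutated WM".

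**The concern.** In a single-arm trial of an add-on, the null stands for the response expected if the added drug does nothing. Here that is the response to ibrutinib alone in CXCR4-mutated disease. The protocol's only genotype-specific figure for it is 61.9%, which is 11.9 percentage points above the null of 50%.

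The stated error rate is controlled only if the background is 50% or lower. If it is nearer 61.9%, the combination can reach 15/20 on ibrutinib's activity more often than 13.2 suggests. Since 13.2 uses 15/20 to decide whether the combination goes on to further evaluation, a declared success could be taken as evidence for the Section 2.4 hypothesis when it does not by itself support it.

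**Working it through.** **Inputs.** From 13.2: n = 20, success at 15 or more, null 0.50, alternative 0.80, power 80%, alpha 0.04, binomial method. From 2.1 and 2.3: 61.9% major response on ibrutinib alone in this genotype.

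**Formula.** With X ~ Binomial(20, p), P(success) = P(X ≥ 15) = Σ C(20, k) p^k (1−p)^(20−k), summed over k = 15 to 20.

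**Reproducing the plan.** At p = 0.80, P(X ≥ 15) = 0.804, which matches the stated power. At p = 0.50, P(X ≥ 15) = 0.0207, and doubling gives 0.0414. The printed 0.04 is therefore the two-sided size, although success is declared only in the upper direction. The one-sided size is 0.021, so the printed figure is conservative and needs only a label.

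**Probability of success with no ulocuplumab effect, by background rate.**

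| Background rate | P(X ≥ 15 of 20) |
|---|---|
| 50% | 0.021 |
| 55% | 0.055 |
| 61.9% | 0.165 |
| 65% | 0.245 |
| 70% | 0.416 |

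At 61.9% the figure is about eight times the one-sided size at 50% (0.165/0.0207 ≈ 8.0) and about four times the printed 0.04 (0.165/0.04 ≈ 4.1).

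**How firm is 61.9%?** The documents do not print the denominator, but it can be recovered.

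- With at most 63 patients, 61.9% and 85.7% can share a denominator only of 21, 42 or 63. The existence of other genotype groups rules out 63.
- With 42, only 21 patients remain. The 91.7% group must then be 11/12, and the group with 60% overall and 0% major response has at least 5 patients. That leaves at most 63 − 42 − 12 − 5 = 4 others, so major responses total at most 26 + 11 + 0 + 4 = 41.
- Section 2.3 reports "very good partial response (n=10); partial response (n=36"), that is 10 + 36 = 46. So 42 is excluded and the figure is 13/21. The split 33/36 + 13/21 + 0/5 gives exactly 46.

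The exact (Clopper-Pearson) 95% interval for 13/21 is 38% to 82%, which includes 50%. Averaging P(X ≥ 15) over this uncertainty gives 0.22 with a uniform prior, posterior Beta(14, 9), and 0.24 with a Jeffreys prior, posterior Beta(13.5, 8.5).

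**What the reported interval would show.** Exact 95% intervals are 50.9% to 91.3% for 15/20, 56.3% to 94.3% for 16/20 and 62.1% to 96.8% for 17/20. The first result to exclude 61.9% is 17/20.

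**What a null of 61.9% would require, keeping 80% as the alternative.**

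| N | Cut-off | One-sided alpha at 61.9% | Power at 80% |
|---|---|---|---|
| 20 | 17 | 0.024 | 0.41 |
| 41 | 31 | 0.047 | 0.82 |
| 54 | 41 | 0.021 | 0.82 |

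N = 41 and N = 54 are the smallest sizes with at least 80% power at one-sided limits of 0.05 and 0.025.

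**The case against.** The strongest reply is that the plan never presents 15/20 as a test against ibrutinib alone. The primary objective is to determine a rate, the comparative wording sits in the rationale, and a null may simply be the rate below which a regimen is dropped. This stands in part: nothing in 13.2 claims superiority over ibrutinib. But 13.2 still sets a null, an alternative, an alpha and a go/no-go rule, and the null needs either to fit the hypothesis or to carry a stated reason.

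The second reply is that 61.9% is too uncertain to show that 50% is wrong. That also stands. The interval for 13/21 contains 50%. The patients were all previously treated, whereas Section 3.1 does not require prior therapy, and the documents do not say which way that would shift the rate. Across the whole interval of 38% to 82%, the false-success probability would run from about 0.1% to about 86%. This argues for showing the rule's behaviour over a range; it does not supply the missing reason for 50%.

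Delayed major responses in this genotype (beyond 6 months, Sections 2.1 and 2.3) might support a lower null at an early fixed assessment. The documents do not make that argument, and the primary endpoint in 13.5 has no time point.

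Finally, 13.5 requires a 95% confidence interval, which a reader could set against 61.9%. That helps interpretation, but at 15/20 the interval includes 61.9% while 13.2 would still declare success. And since Phase II never opened (Sections 1.1 and 5.1), the rule was never applied.

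**Conclusion.** The concern holds, as a point about the design as written. The null of 50% lies below the protocol's own ibrutinib-alone estimate for the enrolled genotype and no reason is given. If that estimate is the true background rate, the chance of declaring success with no ulocuplumab effect is 16%, against 2.1% at the stated null; the 2% to 42% range covers assumed backgrounds of 50% to 70%. These figures are conditional on the background rate, which rests on 13 of 21 previously treated patients and may differ in this trial. The sample-size arithmetic itself is sound, and the alpha point is one of labelling only. It should be fixed because the rule decides further evaluation and the remedy is cheap.

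**What to change.** In Section 13.2, keep n=20 and the 15/20 rule, and:

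1. State the error rates as one-sided exact alpha 0.021 (two-sided 0.041), power 0.80.
2. Give the reason for the 50% null.
3. Print the probability of a false success if the ibrutinib-alone rate is 55%, 61.9% or 70%: 0.06, 0.16 and 0.42.
4. Add a sentence such as: *A result of 15/20 (exact 95% CI 50.9% to 91.3%) shows a rate above 50%; it does not by itself show a gain over ibrutinib alone.*

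These are wording changes in one section. Their cost is that the stated operating characteristics and the permitted conclusion become less favourable.

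Moving the null to 61.9% is a separate trade-off for the sponsor. It would either cut power at 80% from 0.80 to 0.41 at n=20 (with 17/20 required), or add 21 patients (41 − 20) to 34 patients (54 − 20) to keep about 80% power.

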## 13.3 Stratification Factors

No stratification factors will be applied for either the Phase I or Phase II portion of the study.

### **13.4 Interim Monitoring Plan**

The study will be monitored by the DFCI Data Safety Monitoring Committee (DSMC). The DSMC will meet at least two times a year and more often if needed (e.g., for safety review). For each meeting, the study will be reviewed for safety and progress toward completion. Copies of the toxicity reports prepared by the DSMC meetings will be distributed to the Principal Investigator. The Principal Investigator will then distribute to subinvestigators. Any DSMC recommendations for changes to the study will be distributed to the Principal Investigator and then circulated to sub-investigators by the Principal Investigator. No interim analysis of the outcome data is planned.

After the first six participants are accrued to the Phase II cohort, enrollment will be held to conduct a DSMC safety analysis of the first two cycles of treatment. The DSMC will determine if there have been excessive dose reductions or delays which require an amendment to the Phase II ulocuplumab dose level.

### **13.5 Analysis of Primary Endpoints**

The primary objective of the Phase I portion of the protocol is to determine the MTD of ulocuplumab combined with ibrutinib. The maximum tolerated dose (MTD) will be the dose that produces a DLT or the maximum dose allowed by protocol (1600 mg) if no DLT is observed (see section 13.1).

Participants from the Phase II portion of the protocol will be included in the Full Analysis Set (FAS) for the primary assessment of efficacy. The FAS will include those participants who have received at least one dose of therapy.

Primary analyses will be performed in FAS population and will include calculating the proportion of patients having a major response (PR or better). Confidence intervals (95%) around these point estimates will be presented.

### **13.6 Analysis of Secondary Endpoints**

The Per-Protocol Analysis Set (PPS) is defined as all participants from the FAS set who complete the study and are deemed to be protocol-compliant. To be protocol-compliant, a participant must not have any major protocol deviations during the study period. Protocol deviations will be identified prior to database lock and will be listed in the clinical study report. The PPS will be used for secondary assessment of efficacy endpoints.

Secondary analyses will be performed in both the FAS and PPS populations. There are no secondary endpoints for the Phase I portion of the protocol. For the Phase II participants the time to response, both major (PR or better) and minor response will be estimated using Kaplan Meier methodology with median time plus 25th and 75th percentile time to response along with 95% confidence intervals being provided, as appropriate. Time to progression (TTP) will also be estimated using Kaplan Meier methodology. Best overall response and Very Good Partial Response (>90% reduction in disease burden)/ CR (complete response) will be estimated in both

the FAS and PPS populations involving calculating the proportion of patients having an overall response (MR or better). Confidence intervals (95%) around these point estimates will be presented.

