CT-defined adenopathy ( $\geq 1.5$  cm) was present in 37 patients at baseline. Serial imaging for 35 patients showed decreased or resolved (n=25; 67.6%); stable (n=9; 24.3%); or increased (n=1; n=2.9%) adenopathy. Two patients came off study before repeat imaging was required. Among 7 patients with CT-defined splenomegaly ( $\geq 15$  cm), spleen size was decreased (n=4; 57.1%), stable (n=2; 28.6%), or not evaluable (n=1; 14.3%) following elective splenectomy. Nine patients (14.3%), 3 with positive anti-MAG antibodies, received ibrutinib for progressive IgM-related peripheral sensory neuropathy. All responded, and subjective improvements in peripheral sensory neuropathy occurred in 5, and remained stable in 4 during the treatment course. Symptomatic hyperviscosity related to progressive disease that required plasmapheresis prompted start of ibrutinib in 4 patients. All responded, and none required additional plasmapheresis by the end of Cycle 2. One patient required plasmapheresis for acquired Factor VIII deficiency. He responded, and did not require further plasmapheresis. The spontaneous bleeding events that prompted therapy also resolved. With a median on treatment duration of 19.1 (range 0.5-29.7) months, 43 patients (68.3%) remained on therapy. Reasons for treatment discontinuation included non-response (n=1); progressive disease (n=7); treatment-aggravated thrombocytopenia (n=1); hematoma after BM biopsy (n=1); prolonged drug hold for infection unrelated to ibrutinib (n=1); myelodysplasia/acute myeloid leukemia associated with baseline 5q- deletion related to prior therapies (n=1); disease transformation possibly related to prior nucleoside analogue therapy (n=2); antineoplastic therapy for rectal carcinoma (n=1); ibrutinib incompatible medication (n=1), patient decision to use commercially sourced ibrutinib (n=2), travel difficulties (n=1), and alternative therapy (n=1). The estimated progression-free and overall survival at 24 months was 69.1% (95% CI 53.2%-80.5%) and 95.2% (95% CI 86.0-98.4%), respectively. For patients with progressive disease, the median time to progression was 9.6 (range: 3.5 – 19.4) months if transformation cases were censored, and 9.5 (range: 3.5 – 19.4) months if transformation events were included. Subset analysis showed that >3 prior lines of therapy, high pre-therapy IPSS score, and MYD88WTCXCR4WT mutation status associated with inferior progression-free survival.

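### Time to major response is planned by Kaplan-Meier with no competing-event rule, which can overstate the upper part of the response curve

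*Combined protocol and SAP*

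**What the plan says.** Section 13.6 (Analysis of Secondary Endpoints) states that time to major and "minor response will be estimated using Kaplan Meier methodology with median time plus" the 25th and 75th percentiles; it closes the list with "percentile time to response along with 95% confidence intervals being provided, as appropriate". The analysis is not limited to responders: "Secondary analyses will be performed in both the FAS and PPS populations", and in Section 13.5 "The FAS will include those participants who have received at least one dose of therapy". No section gives a censoring rule for this endpoint, names a competing event or plans a cumulative incidence estimate.

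Three other provisions decide what happens to a participant who has not yet responded:

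- Section 5.8 lists progression among the reasons for ending protocol therapy, though it lets the investigator keep a benefiting participant on treatment.
- Sections 5.9 and 13.2 end follow-up at progression, new anti-neoplastic therapy or death, among other reasons.
- Section 11.1.2 treats IgM as unevaluable for response during a drug hold of more than 7 days and requires more than 2 consecutive weeks on drug for an IgM response assessment.

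Response rates themselves are planned as simple proportions with 95% confidence intervals (Sections 13.5 and 13.6).

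**The concern.** A participant who progresses, dies or stops for good before responding will normally not be seen to respond later. For time to response these are competing events. Kaplan-Meier run in the ordinary way removes such a participant from the risk set and assumes the same future chance of response as for those who remain. One minus the Kaplan-Meier curve then exceeds the proportion that has responded.

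The error grows when responses come late and non-responders leave early. The documents give reason to expect late responses. For CXCR4-mutated disease on ibrutinib alone, Sections 2.1 and 2.3 report a major response rate of 61.9% and major responses delayed beyond 6 months. Faster response is part of the study hypothesis (Sections 2.2 and 2.4), and time to response is a secondary objective (Section 1.3). At stake is a published curve, and possibly a 75th percentile, that the cohort did not reach, printed beside a simple response proportion that disagrees with it.

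**Working it through.** **1. The plan's own figure.** Section 13.2 gives "A maximum of 20 evaluable patients will be accrued for the phase II study" and "Assuming an H0 of major response rate of 50% vs. an H1 of 80"%, with success at 15 or more, and claims "power of 80% with an alpha of 0.04 to detect a difference". With X binomial(20, p):

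- P(X ≥ 15 | p = 0.80) = 0.804, which reproduces the stated power.
- P(X ≥ 15 | p = 0.50) = 0.0207. Doubled, this is 0.041, so the stated alpha is reproduced as a two-sided value.

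**2. How often a 75th percentile is real.** With 20 participants the cumulative incidence reaches 75% only if at least 15 respond. The same binomial tail gives:

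| Endpoint and true rate | P(at least 15 of 20) |
|---|---|
| Major, 50% (null) | 2.1% |
| Major, 61.9% (ibrutinib alone, CXCR4-mutated) | 16.5% |
| Major, 80% (alternative) | 80.4% |
| Minor or better, 85.7% (ibrutinib alone, CXCR4-mutated) | 94.5% |

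**3. A hand example (invented data).** Twelve of 20 respond, at months 1, 1, 2, 2, 3, 4, 6, 7, 8, 9, 10 and 12. Six non-responders leave at months 2.5, 3.5, 5, 6.5, 7.5 and 8.5, and two stay to the end. With the leavers censored:

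S = (16/20)(14/15)(12/13)(10/11)(8/9)(6/7)(4/5)(3/4)(2/3) = 0.191

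One minus Kaplan-Meier is 0.81, and a 75th percentile of 12 months is printed. The cumulative incidence is 12/20 = 0.60 and has no 75th percentile. If all eight non-responders stay to the end, Kaplan-Meier also gives 0.60.

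**4. Simulated cohorts of 20, major response.** Inputs from the documents: a response rate of 61.9%, and treatment of 47 × 4 = 188 weeks, about 43 months. Assumptions: exponential response times with a 6-month median, and the share and timing of non-responders who leave (exponential times, censored when they leave). The 9.6-month median is borrowed from time to progression among patients who progressed (Section 2.3).

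| Non-responders who leave early | Mean 1 − KM at end | Trials printing a 75th percentile |
|---|---|---|
| None | 62% | about 16% |
| Half, median 18 months | 66% | 24% |
| Half, median 9.6 months | about 69% | about 31% |
| All, median 18 months | 74% | 48% |
| All, median 9.5 months | 84% | 76% |

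In every row about 16% of cohorts truly have 15 responders. The third row becomes 70% and 34% if responses beyond the 43-month horizon are moved inside it.

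**5. Where the effect is smaller.**

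- *Median time to major response.* If half leave, it is 11.5 months by Kaplan-Meier and 11.9 by cumulative incidence. If all leave at a median of 9.5 months, it is 10.2 and 11.8. At the 80% alternative it is 7.7 and 7.8.
- *Major response at an 8-week median, half leaving.* The plateau is 65%, and a 75th percentile is printed in 20% of trials.
- *Minor-or-better response, 85.7%, 4-week median.* The plateau is 87% if half leave and 88% if all leave (median 9.6 months). A 75th percentile is printed in 95% to 96% of trials and is real in about 95%.
- *Major response at 80%, half leaving at 9.6 months.* The plateau is 86%, and a 75th percentile is printed in 90% of trials and real in 80%. In the extreme case where all leave, the plateau is 95%.

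**The case against.** The strongest reply is that a reader might infer from Section 13.6 that early leavers are to be censored, and it does not say so. This stands: the text gives no rule, and censoring is what the named method does by default. If non-responders remain under observation, or are carried to the maximum follow-up time, the bias is nil.

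The stopping patterns can also be challenged. In the ibrutinib study that the protocol summarises, "43 patients (68.3%) remained on therapy" at a median treatment duration of 19.1 months. That covers all 63 patients, all genotypes and responders too. Only one stop is listed as non-response and seven as progression; others include travel and a switch to commercial drug. It is not a rate of leaving before response in CXCR4-mutated disease. The rows in which every non-responder leaves are therefore upper cases. They also remove minor responders, who may be benefiting (85.7% − 61.9% = 23.8% of participants).

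Leaving the risk set is not absolute either: Section 5.8 allows treatment beyond progression, and Section 6 allows ibrutinib alone after ulocuplumab stops.

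Finally, the planned simple proportions would show the true rate beside the curve, and the closing qualifier in Section 13.6 lets a percentile be left out. Both soften the problem. Neither prevents a percentile that the cohort did not reach, because the software would return a finite value.

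**Conclusion.** The point holds for major response and for the upper part of the curve. If half of non-responders leave early, the plateau rises from 62% to about 69%, and the chance of printing a 75th percentile roughly doubles, from 16% to 31%. The 74% to 84% plateaus require every non-responder to leave. All of this rests on assumed stopping patterns and exponential times; the documents do not give the stopping fractions for CXCR4-mutated patients.

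Two stronger readings are tempting. One is that most cohorts would never reach a 75th percentile. That is true for major response at 50% or 61.9% (98% and 84% fall short), but not at the 80% alternative (20%) or for minor-or-better response at 85.7% (about 6%). The other is that the quoted median is badly shortened. It moves by 0.4 months if half leave (11.9 − 11.5) and by 1.6 months in the extreme case (11.8 − 10.2).

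This is a descriptive secondary summary. The primary endpoint and the 15-of-20 rule do not use it. Section 1.1 records that Phase II never opened, and Section 13.6 gives Phase I no secondary endpoints, so no result of this trial changes. The defect lies in the plan as written and would carry into any reuse.

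**What to change.** In Section 13.6, replace Kaplan-Meier for time to major and minor response with cumulative incidence (Aalen-Johansen). Treat progression, death, new anti-neoplastic therapy or permanent discontinuation before response as competing events, and censor only participants still under observation without response at the data cut. State how a response is counted in a participant who continues treatment after progression under Section 5.8. Report a percentile only if the cumulative incidence reaches it. Give the median time among responders as a separate figure, labelled as such.

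The cost is a few sentences in the plan and standard software; no extra data or participants are needed. The response curve would look slightly less favourable, and its end point would agree with the simple response proportion when follow-up is complete.
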